6.3.2. Exclusion Criteria

Subjects may not be enrolled into the study if ANY of the following apply:

- Currently pregnant or lactating (subjects who become pregnant during the study will be discontinued).
- Any systemic disease, autoimmune disease, or use of medication, which may interfere with contact lens wear. This may include, but not be limited to, diabetes, hyperthyroidism, recurrent herpes simplex/zoster, Sjögren's syndrome, xerophthalmia, acne rosacea, Stevens-Johnson syndrome, and immunosuppressive diseases or any infectious diseases (e.g. hepatitis, tuberculosis).
- The use of systemic or ocular medications that would contraindicate contact lens wear.

- Entropion, ectropion, extrusions, chalazia, recurrent styes, glaucoma, history of recurrent corneal erosions, aphakia, or moderate or above corneal distortion by keratometry.
- Any previous, or planned, ocular or interocular surgery (e.g., radial keratotomy, photorefractive keratectomy (PRK), laser in situ keratomileusis (LASIK), etc.).
- Any grade 2 or greater slit lamp findings for corneal staining, and any grade 3 or greater slit lamp findings for other abnormalities (e.g., edema, corneal neovascularization, tarsal abnormalities, conjunctival injection) on the ISO 11980 classification scale, any current inflammatory events or events within the last 6 months, or any other ocular abnormality that may contraindicate contact lens wear.
- Any known hypersensitivity or allergic reaction to Biotrue or ClearCare contact lens care solutions
- Any ocular infection, allergy or clinically significant ocular disease (e.g. corneal edema, uveitis, severe keratoconjunctivitis sicca, ocular hypertension), or ocular conditions (e.g. strabismus), which might interfere with the study.
- Any corneal distortion resulting from previous hard or rigid gas permeable contact lens wear.
- Extended wear, monovision or multi-focal contact lens correction.
- Participation in any contact lens or lens care product clinical trial within 30 days prior to study enrollment.
- Any subject where the randomized lens demonstrates a fit that is deemed inappropriate by the investigator, including, but not limited to, the lens being too flat, too steep, have excessive or inadequate movement, and/or insufficient limbal coverage.
- Employee or relative of employees of sponsor or investigational clinic (e.g., Investigator, Coordinator, Technician)

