6. DESIGN OF THE CLINICAL INVESTIGATION

6.1. GENERAL

6.1.1. Study Design

This is a three-month, open-label, bilateral, parallel group, randomized, daily wear contact lens dispensing study comparing the Qualis Silicone Hydrogel Soft Contact Lens for Daily Wear with the currently marketed Acuvue Vita (senofilcon C) Monthly Contact Lens (FDA cleared under K160212). Eligible subjects will be examined for baseline evaluation and lens fitting. Up to fifty (50) subjects will wear the test contact lenses and up to twenty-five (25) subjects will wear the control contact lenses. The subjects will undergo standard ophthalmic evaluation for contact lens wear and will be followed for a period of ninety days.

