6.3.4. Point of Enrollment

The investigational site will screen subjects to determine if each subject is eligible to participate in the investigation. Pre-screening of basic eligibility may occur prior to the initial visit; however, Subjects are required to complete the informed consent process prior to the baseline/screening visit (Visit 1). All subjects who sign an Informed Consent form and meet the eligibility criteria during the screening visit are defined as “enrolled” into the clinical investigation regardless of any further participation.

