6.4.3. Study Procedures

At the first visit after informed consent has been given, the investigator will review the subject's medical history, ocular history (including concomitant treatments), demographics and contact lens wear history. The subject will complete a baseline symptoms questionnaire. A series of routine optometric assessments and tests will be conducted to evaluate the subject's ocular health and refractive status. This will include measurement of manifest spherocylindrical refraction, best sphere refraction and resultant visual acuity, keratometry, and biomicroscopy (slit-lamp examination). Once it has been verified that the subject meets the inclusion / exclusion criteria the test lens parameters will be determined based on Rx. The lens parameters will be recorded, and the subject will be randomized to receive the test or control lenses, which will be dispensed from a stock at the site. After insertion of the study lenses the fit and visual acuity will be evaluated and an over-refraction with visual acuity will be performed. The subject will be educated on safe contact lens use, and will be instructed to wear the study lenses on a one-month replacement schedule for at least 6 hours a day for a minimum of 5 days per week. The subject will be provided with Biotrue or ClearCare for routine cleaning, disinfection and storage; and will be educated on the daily care regimen for the study lenses. At the conclusion of the visit, follow-up visits will be scheduled.

There will be five scheduled follow-up visits during the treatment period at the following intervals: 7 days, 14 days, 30 days, 60 days, and 91 days. During these follow-up visits any changes to medical history will be reviewed, the subject will complete a symptom questionnaire, and a series of routine optometric assessments

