6.4.7. Clinical Parameters

All procedures for the study are routine procedures that are performed as part of standard clinical care.

Visit 1: Screening/Enrollment/Baseline/Lens Dispense

Investigators will adhere to the following routine:

- Explanation of the study*
- Signing of the consent form*
- Assignment of the subject identification number
- Demographics and ocular history questionnaire
- Concomitant treatments
- Habitual contact lens wearing history
- Comfort, vision, and handling questionnaire
- Symptoms questionnaire
- Manifest spherocylindrical and best sphere refraction
- Visual acuity (LogMAR) with spectacle refraction
- Keratometry
- Slit lamp biomicroscopy examination to evaluate ocular integrity (limbal redness, bulbar redness, corneal staining, corneal infiltrates, other findings; GPC, vascularization, edema/striae, microcysts, pinguecula, etc.)
- Review of inclusion and exclusion criteria / eligibility determination
- For subjects that fail to meet enrolment criteria, document the screening failure
- For subjects that meet the study criteria document their enrolment, assign a subject ID, and apply the subject ID to the Subject Randomization List. Determine the applicable contact lens power based on Rx and dispense lenses.

~ **INSERT** study lenses and wait 5 minutes~

- Visual acuity (LogMAR) and over-refraction with dispensed contact lenses
- Slit lamp evaluation for contact lens fit and contact lens surface quality

- Instruction on contact lens care and use
- Adverse event identification and reporting
- Device deficiency reporting
- Protocol deviation reporting
- Schedule follow up visit(s)*

* May be completed remotely.

Visit 2, 3, 4, and 5: Follow Up Visit – Day 7, Day 14, Day 30, and Day 60.

Investigators will adhere to the following routine:

~ subject is instructed to wear study lenses at the visit ~

- Update medical history/concomitant treatments questionnaire*
- Comfort, vision, and handling questionnaire*
- Symptoms questionnaire*
- Visual acuity (LogMAR) and over-refraction with dispensed contact lenses
- Slit lamp evaluation for contact lens fit and contact lens surface quality

~ REMOVE study lenses~

- Slit lamp biomicroscopy examination to evaluate ocular integrity (limbal redness, bulbar redness, corneal staining, corneal infiltrates, other findings; GPC, vascularization, edema/striae, microcysts, pinguecula, etc.)
- Manifest spherocylindrical and best sphere refraction

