6.4.8. Study Completion Procedures

A study exit form must be completed for all subjects.

Subject Completion:

Subjects are considered to have completed the study if they have completed follow-up examinations through the 91-day study period and when all of the study procedures have been completed. All completed subjects’ data will be considered evaluable unless a significant protocol deviation was reported. Written justification will be required for the use of data in the evaluation of the safety and/or efficacy of study product from any subject found to have a protocol deviation.

Subject Discontinuation:

Possible reasons for discontinuation include:

1. Screen Failure – the subject does not meet the protocol specified inclusion criteria or has one or more of the exclusion criteria present.
2. Adverse Event – the subject has been reported to have an adverse event and was discontinued due to the adverse event.
3. Subject Decision – the subject decides for whatever reason to exit from the study. The reason must be recorded in the comments section of the Exit Form.
4. Investigator, Sponsor or IRB Decision – the subject is exited from the study based on a decision by the investigator the Sponsor or the reviewing IRB. The reason for discontinuation must be recorded in the comments section of the Exit Form.
5. Protocol Violation – the subject or the investigator is repeatedly found to be in violation of the study protocol.

Subjects may be discontinued from the study at the discretion of the investigator only for reasons related to the study treatment regimen that would jeopardize the subjects' health and/or welfare if they were to continue in the study.

Discontinued subjects will be considered to have completed the study and should not be replaced. However, every effort will be made to follow discontinued subjects to obtain as much follow-up data as possible regarding the subject's current visual status until the planned end of the study period.

NOTE: The Investigator will immediately (within 2 working days) notify Monitor/CRO if a subject discontinues from the study.

Subjects Lost to Follow-up:

Subjects may be lost to follow-up from the study for non-treatment related reasons. Reasons for loss to follow-up include, but are not necessarily limited to:

- 1) voluntary withdrawal from the study by the subject;
- 2) subject has moved from the area; or
- 3) subject is unwilling or unable to return for follow-up.

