Lens fitting characteristics will be assessed with the lens on-eye and utilizing the biomicroscope with low magnification (X10 to X16) and white light with a diffuser. Lens centration and overall lens fit/movement will be assessed at all visits.

Lens centration

Using a slit lamp with white light, a diffuse and/or broad beam and low-medium magnification, the lens centration of the right and left contact lenses should be evaluated with the eye in the primary position (relaxed, looking straight ahead) and assessed as follows:

Lens Centration Grading Scale

0	Optimal lens centration
1	Acceptable decentration
2	Unacceptable decentration
3	Corneal exposure

Overall lens fit / movement

Using a slit lamp with white light, a diffuse and/or broad beam and low-medium magnification, the movement of the right and left contact lenses should be evaluated a) immediately after the blink with the eye in the primary position and if necessary b) recovery following digitally applied lower lid margin push-up with the lower lid and then fit assessed as follows:

Overall Lens Fit / Movement Grading Scale

-2	Unacceptably tight (reduced movement, unacceptable)
-1	Acceptably tight (reduced movement, acceptable)
0	Optimal fit / movement
+1	Acceptable loose (excessive movement, acceptable)
+2	Unacceptable loose (excessive movement, unacceptable)

Note: +2 and -2 are NOT acceptable for study eligibility.

Keratometry Reading

Corneal curvature measurement using a standard keratometer will be performed at all visits. It is essential that best alignment is achieved prior to taking the measurement and the subject opens the

eye as wide as possible. The methodology recommended by the manufacturer will be used. When possible the same operator/technician should use the same equipment at all visits to obtain consistent readings. This measurement will provide corneal curvature measurements. Steep and Flat K readings and axis will be recorded. Readings for this study are required in Diopter (D) for all visits and additionally in mm at baseline visit for contact lens base curve parameter.

Appendix 3

Case Report Forms

Screening/Enrolment/Baseline/Lens Dispense Visit Case Report Form

Screening/Enrolment/Baseline/Lens Dispense Visit Form

Subject ID: _____

Date: ____/____/_____ (MM/DD/YYYY)

Collection Start Time: ____:____ (HH:MM, 24h)

Principal Investigator: _____

Clinical Investigator: _____

Subject Sex: Male Female

Subject Age: _____

Subject Ethnicity:

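### Unacceptable fit of the randomized lens is written as an exclusion but judged after open-label randomization, and the plan conflicts on whether such a subject is enrolled

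*Combined protocol and SAP*

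**What the plan says.** **The criterion.** Among the conditions that bar enrolment, section 6.3.2 and the synopsis (1.5) list "Any subject where the randomized lens demonstrates a fit that is deemed inappropriate by the investigator". Appendix 2, under overall lens fit and movement, adds: "Note: +2 and -2 are NOT acceptable for study eligibility".

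**The sequence.** Section 6.1.1 describes a "three-month, open-label, bilateral, parallel group, randomized, daily wear contact lens dispensing study". Section 6.4.3 has the investigator verify the criteria, choose lens parameters and randomize. Only then: "After insertion of the study lenses the fit and visual acuity will be evaluated". The Visit 1 list in 6.4.7 has the same order. Its enrolment step reads "For subjects that meet the study criteria document their enrolment, assign a subject ID, and apply the subject ID to the Subject Randomization List"; dispensing, insertion and the slit-lamp check of fit come afterwards.

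**Status of the subject.** Section 6.3.4 counts as enrolled everyone who has given consent and is found eligible at the screening visit, and this entry is "into the clinical investigation regardless of any further participation". Section 6.4.8 introduces its list with "Possible reasons for discontinuation include", and the first entry is screen failure, defined to include anyone with an exclusion criterion present. It also says that discontinued subjects are not replaced and that every subject needs an exit form. The baseline form in Appendix 3 asks about eligibility before the Dispense tab and again in the End tab, after the fit grades. A negative answer there leads to the Exit Form.

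**Analysis.** Section 7 is descriptive only. It plans a disposition table, a screen-failure table by reason, a listing of subjects left out of key analysis sets, tables by treatment and overall, and safety reporting on all enrolled subjects. Discontinuations and their reasons are a secondary outcome (6.1.3).

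**The concern.** An exclusion criterion should be decidable before assignment. This one cannot be, because it concerns how the assigned lens behaves on the eye and is judged by someone who knows which lens it is. Applied as written, it can remove a randomized subject who has worn the study lens, for a reason that the lens itself produced. That is a result of treatment, not a baseline characteristic.

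The text does not settle how such a subject is counted, and two sites could follow it faithfully and classify the same case differently. One would record a screen failure who was never enrolled, the other a discontinuation in the assigned arm. With no hypothesis test, the reported counts and percentages are the evidence for comparability with the marketed lens, so their numerators and denominators need to be unambiguous.

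**Working it through.** **1. The plan's own figure.** Section 6.3.6 plans up to 50 test and up to 25 control subjects: 50 + 25 = 75, as stated. The number is taken from guidance, so there is no power calculation to reproduce.

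**2. The passages side by side.**

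| Points to not enrolled | Points to enrolled |
|---|---|
| 6.3.2 and synopsis: fit sits among conditions that bar enrolment | 6.4.7: enrolment and the randomization-list entry are documented before insertion |
| Appendix 2 note: the two extreme fit grades fail eligibility | 6.3.4: enrolment holds whatever happens later |
| End tab: eligibility is asked again after fit is graded | 6.4.8: screen failure is itself a type of discontinuation, not replaced, with an exit form |
| Section 7: screen failures have their own table | Section 7: disposition and tables by treatment |

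Section 6.3.4 does not break the tie, because it requires the eligibility criteria to be met during the screening visit and fit is assessed at that same visit. No passage says that a fit failure after randomization is counted in the assigned arm.

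**3. Effect of omitting one subject.** Let n be the arm size and d the number of other discontinuations. Counting the fit failure gives a rate of (d+1)/n. The reduction if it is left out is:

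- numerator only: (d+1)/n − d/n = 1/n
- numerator and denominator: (d+1)/n − d/(n−1) = (1/n)(1 − d/(n−1)), at most 1/n
- left out and another subject enrolled instead: (d+1)/(n+1) − d/n = (n−d)/(n(n+1)), below 1/n

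So the bound per subject is 1/n for any d: 1/50 = 2.0 percentage points (test) and 1/25 = 4.0 points (control).

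**4. Illustration under assumptions.** The documents give no fit-failure rate and no expected discontinuations. Assume 2 other discontinuations among 50 test subjects.

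| Fit failures (assumed) | Counted in arm | Removed from numerator and denominator |
|---|---|---|
| 1 | 3/50 = 6.0% | 2/49 = 4.1% |
| 3 | 5/50 = 10.0% | 2/47 = 4.3% |
| 5 | 7/50 = 14.0% | 2/45 = 4.4% |

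The chance of at least one case is 1 − (1−p)^n. For assumed p of 2%, 5% and 10% it is 64%, 92% and 99.5% among 50 test subjects, and 40%, 72% and 93% among 25 controls.

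**The case against.** The strongest reply is that the operational text already favours the enrolled reading. Enrolment is documented before insertion (6.4.7) and holds regardless of later participation (6.3.4). A negative End-tab answer leads to an Exit Form that offers dispensing as the exit visit. Section 6.4.8 makes even a screen failure a discontinuation that is not replaced. Section 7 tabulates by treatment and reports safety on all enrolled subjects, and Section 14 requires every adverse event to be reported whatever its classification. A subject who leaves at dispensing also has little post-insertion data beyond adverse events and fit.

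Most of this stands, and it limits what can be claimed. A reader might infer that these subjects will vanish from the discontinuation count, be replaced, or drop out of safety reporting. The documents do not show that. Each is possible only if the lead-in of 6.3.2 and the separate screen-failure table are allowed to prevail.

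Three further inferences also fail:

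- **The rule favours the test lens.** The criterion applies to both lenses, and no fit-failure rates are given.
- **The Exit Form cannot record the case.** It offers lens positioning, investigator decision and a free-text other.
- **Section 13's bar on exposure before the criteria are passed is breached.** It refers to screening criteria and does not say whether fit is one of them.

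The reply does not remove the core problem. The criterion is still written as a bar to enrolment, the End tab still acts on it after assignment, and the favourable reading has to be pieced together from several sections.

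**Conclusion.** The point holds and should be fixed. The rule itself is at fault: unacceptable fit is a post-randomization event that depends on the assigned lens, it is judged open-label, and it is listed as an eligibility exclusion. The plan conflicts on whether the subject is enrolled.

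The size is bounded per subject only, at 2.0 points of discontinuation rate in the test arm and 4.0 in the control arm. That bound applies if such subjects are handled as not enrolled and the arms reach 50 and 25. Those figures are ceilings, and a smaller arm would give a larger step. Total effect and direction are unknown. The illustrative percentages rest on assumed counts and are not predictions. No test or margin is affected, because the plan has none, and adverse event reporting does not turn on this point.

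**What to change.** Leave the clinical fit rule and the grade threshold as they are, and change how the event is classified and counted:

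1. In 6.3.2 and the synopsis, move the fit item out from under the lead-in that bars enrolment and make it a reason for discontinuation after randomization.
2. In 6.3.4, 6.4.8 and Section 7, state that a randomized subject is enrolled and is not replaced, and that unacceptable fit found after randomization is a discontinuation, not a screen failure.
3. In Section 7, state that disposition and discontinuations are tabulated by assigned lens over all randomized subjects.
4. Keep the safety set as all enrolled subjects, and say that it includes every randomized subject.
5. Reconcile the Appendix 2 note and the End-tab eligibility question with the above.

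The cost is a wording amendment and one form question. No visit or measurement is added, because randomization group, lens type, fit grade and exit visit are already recorded. The downside is that discontinuation rates may look slightly less favourable in either arm.

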6.3.3. Subject Withdrawal or Discontinuation

Refer to section 6.4.6 for information regarding subject withdrawal or discontinuation.

6.3.4. Point of Enrollment

The investigational site will screen subjects to determine if each subject is eligible to participate in the investigation. Pre-screening of basic eligibility may occur prior to the initial visit; however, Subjects are required to complete the informed consent process prior to the baseline/screening visit (Visit 1). All subjects who sign an Informed Consent form and meet the eligibility criteria during the screening visit are defined as “enrolled” into the clinical investigation regardless of any further participation.

6.3.5. Duration of the Clinical Investigation

The total duration of treatment will be at least 91 days from lens dispensing for each individual subject.

6.3.6. Number of Subjects Required

To ensure a minimum of 50 completed subjects (with 30 completed subjects in the test arm), 75 subjects will be enrolled to participate. Up to fifty (50) subjects will wear the test contact lenses and up to twenty-five (25) subjects will wear the control contact lenses.

The number of subjects was determined based on the recommendations in *Premarket Notification [510(k)] Guidance Document for Class II Daily Wear Contact Lenses*.

6.3.7. Enrolment Period

The estimated enrolment period for this investigation is forty-five (45) days.

6.3.8. Subject Payment

Subjects in will be paid a specified amount in return for their time and travel to the clinic to attend the six (6) scheduled study visits. If participation ends prior to completing all study visits, this payment will be prorated accordingly. If interim or additional visits are required, the subject will receive an additional \$50 USD per visit.

6.4. PROCEDURES

6.4.1. Enrolment Procedures

Each subject who is considered for the investigation must be presented with the Informed Consent document and must read the document or have the document read to them. The investigator or an authorized, delegated member of the investigational staff will explain the study purpose, procedures, and subject responsibilities to the potential participant. Subjects will be informed that their participation is voluntary and that they may withdraw consent to participate at any time. They will be informed that choosing not to participate will not affect the care the subject will receive. Finally, they will be told that if needed their records may be accessed by the health (regulatory) authorities, the IRB, and authorized sponsor and CRO staff without violating the confidentiality of the subject, to the extent permitted by the applicable law(s) or regulations. The subjects' willingness and ability to meet the follow-up requirements will be determined. The subject will be given sufficient time to read the informed consent form and

the opportunity to ask questions. The subject will sign and date the informed consent form. The investigator will also sign and date the consent form. The original informed consent form will be retained with the subject records and a copy will be provided to the subject. An Affidavit of Informed Consent will be completed for the clinical monitor to confirm that consent was obtained.

